6.3.2. Study Schematic

The study comprises a 12-16 week pre-treatment follow-up period and a 24 week post-treatment follow-up period (Figure 1).

Patient bone marrow will be aspirated about 9-11 weeks following the first screening visit. The MSC isolation and cell propagation process will last about 3-5 weeks and will be followed by MSC-NTF cells transplantation.

At the transplantation visit (about 12-16 weeks after the screening visit), subjects will be admitted to an inpatient study unit for study procedures and will be followed for 44-72 hours post transplantation.

Following treatment patients will be followed at monthly visits for a total of 24 weeks.

Each patient will thus be followed for a total of about 38 weeks (9-10 months) from the first screening visit (Figure 3).

[figure not shown]

Figure 3: Clinical Study flowchart

Clinical study flowchart outlining the pre- and post-transplant follow-up.

6.3.3. Treatment Plan**6.3.3.1. Bone Marrow aspiration procedure:**

Human bone marrow will be aspirated by a credentialed health care provider as per Medical Centre procedures bilaterally from multiple punctures of the iliac crest of the pelvic bone of patients into 20 mL syringes pre-filled with approximately 1.5 mL of a Heparin-containing solution (Heparin Solution, USP, 100 units/mL) diluted 1:20 in HBSS.

Vacutainer tubes (Green cap 6 ml REF 367886 BD or equivalent with Sponsor approval) containing Lithium Heparin Sodium for injection (95 IU units/tube) will be pre-labelled and the cap pre-cleaned with Ethanol. After replacing the aspiration needle with a new sterile 19 gauge needle, the bone marrow aspirated from each single puncture (2-3 ml), will be injected into a separate pre-labelled Vacutainer tube. Immediately after bone marrow is injected into the tube, the tube will be thoroughly mixed to avoid clotting of the bone marrow sample.

A total of 50-70 ml of Bone Marrow will be aspirated from each patient.

6.3.3.2. IT Transplant Procedure

Participants will undergo a lumbar puncture (Spinal needle 20GA 3.50 IN (0.9 x 90 mm) followed by intrathecal injection of cells or placebo (Dulbecco modified Eagle Medium, DMEM). The detailed transplantation procedure is provided in Appendix 3.

6.3.3.3. IM Transplant Procedure

Participants will undergo a unilateral (right) IM transplantation of cells or of placebo solution (DMEM) into 24 sites in the biceps and triceps muscles of the upper arm (Figure 4). The detailed transplantation procedure is provided in Appendix 4.

[figure not shown]
**Figure 4: Study groups flowchart**

Diagram delineating placebo and cells transplantation in the treatment and placebo groups.

6.3.4. Blinding and Randomization

Randomization will be used to avoid bias in the assignment of patients to treatment, to increase the likelihood that known and unknown subject attributes (e.g., demographics and baseline characteristics) are evenly balanced across treatment groups, and to enhance the validity of statistical comparisons.

This is a double-blind study; the investigators, the subjects, and designated study monitors will be blinded to the treatment assignment throughout the subject's participation in the trial. The exceptions to the blinding will be the Production team (unblinded personnel) at the cell culture facility at the site who distribute the MSC-NTF cells, and the unblinded statistician who will create the final randomization schedule but will not otherwise be involved in the trial.

Randomization will be stratified by site. Site-specific randomization lists will be provided to the Production manager prior to any subjects being randomized. The Production manager will refer to the randomization list when assigning treatment to a subject, and will allocate the treatment corresponding to the subject's randomization number. Randomization numbers will be assigned sequentially as subjects are randomized at each site. Randomization will occur at Visit 3 (one week before Bone Marrow aspiration) after eligibility has been confirmed. The subject's randomization number will be recorded in the subject's source documentation and CRFs, and the randomization number will be provided to the cell culture facility in preparation for the MSC isolation and cell propagation process.

In the event that emergency unblinding is necessary, the treatment codes for all subjects, where the treatment code information for each subject will be separated to ensure that all treatment codes will not be unblinded unnecessarily, will be available from the Medical Monitor. The randomization code may be broken only in the event of an emergency when it is essential to know which treatment the subject received in order to provide appropriate care. Whenever the code is broken for safety reasons, the date, time, and reason for unblinding must be documented by the investigator or any other person breaking the code, the Sponsor must be notified immediately.

6.3.5. Duration of study

Participants will be screened and undergo bone marrow aspiration after 9-10 weeks. Following aspiration, cells will be grown in culture for approximately 24-30 days (3-4 weeks). Participants in both the treatment and placebo groups will undergo combined IT and IM cell transplantation with either MSC-NTF cells or the placebo (DMEM). Following cell transplantation, participants will be monitored as inpatients for a period of at least 44 hours. Participants will be discharged after at least 44 hours and up to 72 hours unless a clinical adverse event(s) occur that require continued inpatient monitoring and/or treatment. Each subject's participation in the study will last for approximately 9 months.

6.3.6. Discussion of Dose

The combined IM and IT transplantation dose is the highest dose of MSC-NTF administered by combined intramuscular and intrathecal administration shown to have been safely administered in previous clinical trials in ALS patients (see section 6.1.2 above).

6.3.7. Discussion of Study Design, Including Choice of Control Group

The study is a randomized double blind placebo controlled study. The control group will be given placebo. It is expected that 36 subjects given MSC-NTF and 12 subjects DMEM in the placebo arm will provide an adequate number of subjects to compare rates of adverse events between the treatment and control groups and allow us to explore the effects on the rates of decline on the ALSFRS-R and SVC between the treatment and placebo control groups as well as individual changes from baseline scores through Week 24 following treatment.

One of the study exploratory endpoints is aimed at determining feasibility of succeeding in performing successful IT administration of MSC-NTF cells and of blinding patients and caregivers to the treatment in anticipation of performing a larger Phase III efficacy study.

ALS is a terminal disease, and life expectancy of patients is usually 3 to 5 years after diagnosis of ALS. Early stage ALS patients (≤ 24 months from ALS symptom onset and ALSFRS-R ≥ 30) were therefore chosen as the study population, to increase chances of participants of completing the full 9 months study and to obtain a patient population with a relatively homogenous rate of disease progression thus increasing the power for detecting a difference in the efficacy outcomes (either between treated and controls or change from baseline among treated vs. untreated subjects). Rates of decline on the ALSFRS-R in such patients are reported in the published scientific literature to range from -0.92 ± 0.08 points/month (Castillo-Viguera et al 2010, NEALS data) to 2.35 (Sorenson EJ et al. 2008).

Since ALS is a fatal, progressive, neurodegenerative disease characterized by motor-neuron cell death in the brain and spinal cord, accompanied by rapid loss of muscle control and eventual complete paralysis and there is currently no available treatment to prevent its progressive course, a reduction in the slope of decline in the ALSFRS-R and/or in the SVC reflected as a change in disease progression (slope) compared to concurrent placebo controls will be considered to constitute a response that will be evaluated further in Phase III clinical studies.

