Concomitant and Excluded Therapy	Study participants will be on a stable dose of riluzole for at least 30 days prior to screening or not taking riluzole at all, nor plan to begin riluzole during the study period.
SUBJECT POPULATION	
Number of Subjects Planned	48 total (3:1 randomization with 36 subjects in the active treatment arm and 12 in the placebo arm).
Major Inclusion Criteria	Age 18 to 75 years old. ALS symptom onset defined as first onset of weakness \leq 24 months and ALSFRS-R \geq 30 at the Screening Visit. Upright slow vital capacity (SVC) measure \geq 65% of predicted for gender, height, and age at the Screening Visit.
ASSESSMENTS	
Safety	Tabulation of AEs, changes in physical and neurological examination findings, hematology, serum chemistry, urinalysis, vital signs and requirement of concomitant medications.
Efficacy	The change in slope from the pre-transplantation period to the post-transplantation period in ALSFRS-R scores and slow vital capacity (SVC) through Weeks 12 and 24 post-transplantation for treatment compared to placebo. The change in slope from the pre-transplantation period to the post-transplantation period in ALSFRS-R scores and slow vital capacity (SVC) through Weeks 12 and 24 post-transplantation for each treatment group. The change in slope from the pre-transplantation period to the post-transplantation period in hand held dynamometry (HHD) and EIM (optional) through Weeks 12 and 24 post-transplantation for treatment compared to placebo. The change in slope from the pre-transplantation period to the post-transplantation period in hand held dynamometry (HHD) and EIM (optional) through Weeks 12 and 24 post-transplantation for each treatment group.
For the Schedule of Study Assessments, see Table 1 in Appendix 1.	

STATISTICAL METHODS AND ANALYSIS		

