6.9.4. Statistical Methods and Sample Size Determination

Summaries for continuous variables will include the sample size, mean, standard deviation, median, minimum, and maximum. Minima and maxima will be reported with the same precision as the raw values; means, standard deviations, and medians will be presented to one additional decimal place than reported in the raw values. Summaries for discrete variables will include frequencies and percentages. All percentages will be rounded to one decimal place (i.e., XX.X%). Differences between treatment groups will be calculated as MSC-NTF cells – placebo and change from baseline will be calculated as post-treatment – pre-treatment (OR follow-up visit – baseline: e.g. Week 2 – baseline, Week 4 – baseline). The baseline visit will be defined as the last non-missing measure prior to initiation of investigational treatment. Additionally, for the pre-transplantation period and transplantation visits, change from screening (V1) summaries will be calculated as pre-transplantation period/transplantation visit – screening.

All efficacy analyses will use one-sided alpha = 0.10 tests and present one-sided 90% lower confidence limits and two-sided 95% confidence intervals around the difference between treatments as well as two-sided 95% confidence intervals around the point estimates within each treatment group. All summaries will be presented by treatment group.

A statistical analysis plan (SAP) will be prepared and finalized prior to database lock, unblinding and analysis of study results.

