6.9.4.2. Safety analyses

Primary Objective: The safety of MSC-NTF transplantation via combined IT and IM injection in participants with ALS is the primary objective of this study. Safety endpoints include AEs, changes in physical and neurological examination findings, hematology, serum chemistry, urinalysis, vital signs, and requirement of concomitant medications.

All AEs will be coded to System Organ Class (SOC) and Preferred Term (PT) using the MedDRA®. The number of Treatment-Emergent Adverse Events (TEAEs) and the number of subjects with any TEAEs (along with percentages) will be tabulated by SOC and PT within each SOC by treatment group and over treatment groups. To count the number of subjects with any TEAEs, a subject who experiences multiple TEAEs within the same SOC will be counted only once for that SOC (whether or not the TEAEs are coded to the same PT). A subject who experiences multiple TEAEs coded to the same PT within the same SOC will be counted only once for that particular PT. In the summary, SOC will be listed in ascending alphabetical order; PTs will be listed in order of descending frequency for all subjects within each SOC.

Separate summaries will be provided for the following categories of AEs:

- TEAEs
- TEAEs by severity
- Treatment-related TEAEs
- Serious TEAEs

The proportion of subjects having each AE will be compared between treatment using Fisher's exact tests.

When evaluating changes in safety parameters, baseline will be defined as the last measurement prior to transplantation (i.e., prior to treatment).

Physical examination, neurological examination, hematology, serum chemistry, vital signs and concomitant medications will be summarized using descriptive statistics (n, mean, standard deviation, median, minimum, and maximum) if the data is continuous and using counts and percentages if the data is discrete. Shifts from baseline in categorization of results (e.g. normal/abnormal or low/normal/high) will also be summarized.

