6.9.4.4. Determination of sample size

No formal sample size calculation has been performed. The sample size chosen was not based on statistical considerations. The total of 36 treatment and 12 placebo subjects are expected to be a sufficient number to obtain adequate characterization of common TEAEs and to observe trends for treatment effects on the efficacy measures chosen for this study.

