5 Blood Biochemistry: Na, K, Cl, HCO₃, BUN, Cr, Glucose, Ca, Mg, Phosphorus, total protein, triglycerides (TG), Total cholesterol, HDL, LDL, urea, creatinine, total bilirubin, AST(GOT), ALT(GPT), ALP - Time Window: +/- 2 hours

6 Urinalysis (dip-stick test) - Specific Gravity, pH, glucose, protein, ketones, blood

7 Coagulation PT, PTT

8 Can be done prior to discharge

4. Study Treatment

The investigational products for this study will be

- MSC-NTF cells
- Placebo (Dulbecco Modified Eagle Medium, DMEM)

IT Transplant Procedure: Participants will undergo a lumbar puncture (Spinal needle 20GA 3.50 IN (0.9 x 90 mm)) followed by intrathecal injection of cells or placebo (DMEM).

IM Transplant Procedure: Participants will undergo a unilateral (right) IM transplantation of cells or placebo solution (DMEM) into 24 sites in the upper arm.

The study flowchart described above is shown in Figure 2.

[figure not shown]

Figure 2: Study Groups Flowchart

5. Sample Size

This is a Phase II study for which no formal sample size calculation has been performed. The sample size chosen was not based on statistical considerations. The total of 36 treatment and 12 placebo subjects are expected to be a sufficient number to obtain adequate characterization of common treatment emergent adverse events and to observe trends for treatment effects on the efficacy measures chosen for this study. Additionally, with 36 subjects in the MSC-NTF treatment group, the study has 95% probability of seeing adverse events that occur at a true rate of 8% or greater. Therefore, if an adverse event of a specific type does not occur, there is 95% probability that the true rate of the adverse event is less than 8%.

6. Analysis Populations

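### 36 versus 12 subjects can describe common adverse events but does not support the between-arm rate comparison that protocol 6.3.7 calls adequate; one SAP sentence also misstates a confidence bound

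*Protocol*

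**What the plan says.** The synopsis plans "48 total (3:1 randomization with 36 subjects in the active treatment arm and 12 in the placebo arm". Protocol 6.3.7 expects that these numbers "will provide an adequate number of subjects to compare rates of adverse events between the treatment and control groups". It gives no event rate, detectable difference or power.

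The test is named in protocol 6.9.4.2: "The proportion of subjects having each AE will be compared between treatment using Fisher's exact tests". The synopsis plans the same test.

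Protocol 6.9.4.4 is more modest. It says "No formal sample size calculation has been performed" and that the size has no statistical basis. It then states the safety aim: "The total of 36 treatment and 12 placebo subjects are expected to be a sufficient number to obtain adequate characterization of common TEAEs".

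SAP section 5 (Sample Size) repeats that text and adds the only safety figure in the documents. With 36 treated subjects, "the study has 95% probability of seeing adverse events that occur at a true rate of 8% or greater". It concludes that if an event type does not occur, "there is 95% probability that the true rate of the adverse event is less than 8" percent.

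SAP 10.1.1 tabulates AEs by arm as counts and percentages. It names no between-arm test for them.

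**The concern.** Safety is the primary objective, and 6.3.7 is where the protocol says what the concurrent placebo arm can do for it. A reader told that the numbers are adequate for comparing AE rates may take a non-significant Fisher result as a sign of similar safety. With 12 controls, such a result is the likely outcome even when the excess on active treatment is substantial.

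The SAP's 8% figure does not fill the gap. It answers whether an event would be seen at all among 36 treated subjects, not whether its rate could be told apart from placebo. No figure describes what the 12-subject arm can show.

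**Working it through.** **Inputs.** Arms of 36 and 12 (synopsis; subjects lost before transplantation are replaced, protocol 6.5.3.3, so these are the planned treated numbers). Fisher's exact test per AE (protocol 6.9.4.2). The documents give no alpha, sidedness, power target or AE rates for this test. I therefore assume 80% power, show placebo rates from 0% to 50%, and use two levels: two-sided 0.05, and one-sided 0.10, which the protocol sets for efficacy only ("All efficacy analyses will use one-sided alpha = 0.10 tests").

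**1. The SAP's own figure.** P(at least one event in 36 at a true rate of 8%) = 1 − 0.92^36 = 1 − 0.0497 = 0.950. It reproduces. With 0 of 36 events, the one-sided 95% upper confidence bound solves (1 − p)^36 = 0.05, so p = 1 − 0.05^(1/36) = 7.98%. The number is right. It is a confidence bound, so the 95% belongs to the procedure and is not a probability that the true rate lies below 8%.

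**2. The same calculation for placebo.** 1 − 0.05^(1/12) = 22.1%. An AE with an 8% background rate shows no placebo cases with probability 0.92^12 = 0.37.

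**3. Smallest active-arm count that is significant.**

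| Placebo events | Two-sided 0.05 | One-sided 0.10 |
|---|---|---|
| 0/12 | 10/36 (28%) | 8/36 (22%) |
| 1/12 | 15/36 (42%) | 12/36 (33%) |
| 2/12 | 19/36 (53%) | 16/36 (44%) |
| 3/12 | 22/36 (61%) | 19/36 (53%) |

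In the first row, 9/36 gives two-sided p = 0.088 and 10/36 gives p = 0.048.

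**4. Exact power.** Power = Σ_a Σ_b Bin(a; 36, p_active) × Bin(b; 12, p_placebo), summed over the tables among all 37 × 13 where Fisher rejects with the excess on active. If the placebo rate is 0%, b is always 0 and two-sided power reduces to P(a ≥ 10), which reaches 0.80 at p_active = 33.1%.

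Active-arm rate needed for 80% power:

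| Placebo rate | Two-sided 0.05 | One-sided 0.10 |
|---|---|---|
| 0% | 33% | 27% |
| 5% | 45% | 37% |
| 10% | 54% | 45% |
| 20% | 66% | 58% |
| 30% | 77% | 69% |
| 50% | 91% | 86% |

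Over placebo rates of 0% to 50%, the required excess is about 33 to 47 percentage points at two-sided 0.05 and 27 to 39 at one-sided 0.10.

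**5. Power against moderate excesses**, two-sided 0.05 (one-sided 0.10 in brackets): 10% vs 30%, 23% (41%); 20% vs 40%, 19% (36%); 25% vs 50%, 28% (48%); 10% vs 50%, 72% (88%).

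**6. The 8% event put through the between-arm test.** With 0% on placebo and 8% on active, power is P(a ≥ 10 | 36, 0.08) = 0.04% at two-sided 0.05, and P(a ≥ 8 | 36, 0.08) = 0.7% at one-sided 0.10. So a 95% chance of seeing an event says nothing about distinguishing its rate from placebo.

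**7. Precision.** Approximate 95% half-width of the rate difference at 10% vs 30%: 1.96 × √(0.10 × 0.90/12 + 0.30 × 0.70/36) = 0.226, or 23 points. At 25% vs 50% it is 29 points.

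**The case against.** The strongest reply is that the plan never claims power. The sentence in 6.3.7 is a hedged expectation in a narrative section, with no figure that could be wrong. Protocol 6.9.4.4 and SAP section 5 say openly that the size has no statistical basis and limit the safety aim to characterising common events. The SAP's one figure reproduces. All of this stands.

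The visible SAP also plans only descriptive AE tables, so there may be no Fisher result to misread. That is fair, but it leaves the protocol promising a test that SAP 10.1.1 does not name. The readable bullets of SAP section 13 do not list the change. Some bullets there are redacted, so it cannot be said that the change went undeclared.

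A rare product-related event would be picked up by other routes: its occurrence among 36 treated subjects, investigator causality assessment, the suspension rule in protocol 6.8.4.3 and DSMB review. None of these needs a significant Fisher test, so step 6 shows what the comparison lacks and does not show a hole in safety monitoring. Nor does any passage say that non-significance will be taken as equal safety; that is a risk of interpretation.

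A reader might infer that the main safety claim of the design is wrong, or that the test can detect nothing. The documents support neither. The safety aim in the sample-size sections is descriptive and does not depend on Fisher power, and power against excesses of 20 to 25 points is low (about 19% to 28% at two-sided 0.05) but not nil.

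**Conclusion.** The point holds in a limited form. As a statement about formal between-arm comparison, the adequacy wording in 6.3.7 is unsupported. That conclusion does not hinge on the assumed level: moving from two-sided 0.05 to one-sided 0.10 lowers the required active-arm rates, but they remain at 27% or more. The 80% target and the placebo rates are also assumptions.

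Separately, and without any such assumption, the last sentence of SAP section 5 gives a confidence bound the wrong meaning. The protocol and the visible SAP also differ on whether AEs are tested.

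These are corrections of moderate to low weight. They bear on what may be concluded from the AE tables, not on whether the trial can meet its stated descriptive safety aim.

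**What to change.** 1. **Protocol 6.3.7.** Replace the adequacy statement with a descriptive aim consistent with 6.9.4.4. Give the detectable excess from step 4, with alpha and power labelled as assumed. State that a non-significant AE difference is not evidence of similar safety.
2. **SAP section 5.** Reword the last sentence along these lines: if 0 of 36 subjects have the event, the one-sided 95% upper confidence bound for its rate is 8%. Add the 22% figure for the placebo arm.
3. **SAP 10.1.1.** Report exact 95% confidence intervals for the risk difference for any, serious and treatment-related TEAEs, so that the imprecision is visible. Reconcile with protocol 6.9.4.2 and the synopsis whether AEs are tested by Fisher; if they are, state the level and sidedness.

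The cost is a few sentences, slightly more analysis and a less favourable statement of what the trial can show. It needs no extra subjects and changes no procedure.

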6.4. SUBJECT POPULATION

This study will be conducted in subjects with a clinical diagnosis of ALS who meet the El Escorial criteria (Brooks, B.R., et al 2000) for possible, laboratory-supported probable, probable, or definite ALS. To be enrolled in this study, patients must meet all inclusion criteria in Section 6.4.1 below and must not have any of the exclusion criteria listed in Section 6.4.2.

The subject population is chosen from the group of early-stage ALS participants with the aim of obtaining a homogeneous study population that will facilitate the interpretation of the study results and allow for identifying trends in efficacy outcomes.

Due to the length of the study it is also aimed to include participants that will survive for the duration of the study.

